#### 6.5.1.3 Visit 1.

- Intervention delivery: see 6.5.1.2 Baseline visit
- Return of intervention: refers to the return of research products to the center by the research subject.
- Evaluation of adherence: refers to the assessment made by the IP according to section 6.3.2.1 Procedure to monitor adherence
- Adverse events: see 6.4.3.5 Presence of adverse events
- Intraocular pressure: see 6.4.3.6 Intraocular pressure
- Visual ability: see 6.4.3.1 Visual capacity
- TRL: see 6.4.3.10 Rupture time of the tear film
- Epithelial defects (TF and TVL): see 6.4.3.4.1 Stains
- Eve signs and symptoms: see 6.4.3.4 Eye surface integrity: and 6.4.3.9 Ocular symptomatology
- Vital signs: see 6.4.3.8 Vital signs
- Submission of the subject's diary: see 6.5.1.2 Baseline visit
- Return / daily evaluation of the subject: refers to the delivery of the subject's diary to the IP by the subject. The PI will review the diary to assess its correct filler, evaluate postinstilation symptoms and record applications.
- Continuity assessment of the subject: refers to the determination by the IP and desire of the subject to continue with their participation in the study.

#### 6.5.1.4 Visit 2

- Intervention delivery: see 6.5.1.2 Baseline visit
- Return of intervention: see 6.5.1.3 Visit 1.
- Evaluation of the adherence: it refers to the valuation made by the IP according to the section
- Adverse events: see 6.4.3.5 Presence of adverse events
- Intraocular pressure: see 6.4.3.6 Intraocular pressure
- Visual ability: see 6.4.3.1 Visual capacity
- TRL: see 6.4.3.10 Rupture time of the tear film
- Epithelial defects (TF and TVL): see 6.4.3.4.1 Stains
- Eye signs and symptoms: see 6.4.3.4 Eye surface integrity: and 6.4.3.9 Ocular symptomatology
- Vital signs: see 6.4.3.8 Vital signs
- Submission of the subject's diary: see 6.5.1.2 Baseline visit
- Return / daily evaluation of the subject: see 6.5.1.3 Visit 1.
- Subject's continuity assessment: see 6.5.1.3 Visit 1.

#### 6.5.1.5 Final Visit

Laboratory sample taking: ver 6.4.3.12 Laboratory tests

Sophia Laboratories, S.A. of C.V.

- Pregnancy test: see Pregnancy test
- Return of intervention: see 6.5.1.3 Visit 1.
- Evaluation of the adherence: it refers to the valuation made by the IP according to the section
- Adverse events: see 6.4.3.5 Presence of adverse events
- Intraocular pressure: see 6.4.3.6 Intraocular pressure
- Visual ability: see 6.4.3.1 Visual capacity
- TRL: see 6.4.3.10 Rupture time of the tear film
- Epithelial defects (TF and TVL): see 6.4.3.4.1 Stains
- Eve signs and symptoms: see 6.4.3.4 Eye surface integrity: and 6.4.3.9 Ocular symptomatology
- Subsequent segment; see 6.4.3.7 Subsequent segment
- Vital signs: see 6.4.3.8 Vital signs
- Eye comfort index: see 6.4.3.3 Eye comfort index
- Density of goblet cells (cytology per impression): see 6.4.3.2 Goblet cell density (Cytology per impression)
- Return / daily evaluation of the subject: see 6.5.1.3 Visit 1.
- Return / evaluation of the quality questionnaire: refers to the delivery of the quality questionnaire to the IP by the subject.

6.5.1.6 Security call.

- Adverse events: see 6.4.3.5 Presence of adverse events
- Review of laboratory tests: see 6.5.1.2 Baseline visit .

# 6.5.2 Diagram of the study.

An enrollment time of 30 days is estimated for the total sample.

In order to increase the safety of the participants with the use of the products under investigation, a partial analysis will be carried out following a modification to the Fibonacci method. Said methodology will consist of including 33% of the total sample size (3 subjects per group, n = 9), which will complete all the visits and procedures described. Once this group of 9 subjects has finished their participation in the clinical study, they will proceed to perform a blinded analysis. During the period in which this sub-analysis is carried out, the inclusion of new participants will be restricted. Inclusion will resume when the sponsor notifies each research center.

In addition to safety, the therapeutic adherence will be evaluated and problems related to the procedures will be solved, should they arise.

#### Figure 3. Diagram of the study.

#### 6.6 Sample size.

A total size of 30 subjects is estimated, divided into 3 intervention groups. (10 subjects per group)

#### 6.6.1 Calculation of the sample size.

Although there are no references on the calculation of sample size in phase I studies, it was considered pertinent to perform it according to the presentation of adverse events reported by Hwang HS, et al, in a case-control study in 150 subjects with ophthalmic solutions with Hyaluronate sodium and diquafosol with and without preservative for 3 months. [46].

The percentage of adverse events that occurred with the preservative-free HS solution was 8%, which is why we consider that at least more than 60% of the exposed subjects will not present this rate of adverse events.

The sample size was calculated using the formula for proportions

$$n = \left[ (p1)(p2) + (p1)(p2) \left( \frac{Z_{1-\alpha}}{2} + Z_{1-\beta} \right)^2 \right] / (p1 - p2)^2$$

With a statistical confidence of 95% corresponding to the type I error, equal to 1.96, with a power of 80%, corresponding to the type II error, equal 0.84.

According to the previous calculation, the result is 7.6 subjects (8) per group. The total when considering 3 intervention groups is 24 subjects, which was increased by 25% due to the probable losses. The total sample size required is 30 subjects. Therefore, each group will consist of 10 subjects, who will provide both eyes for the analysis, so that the total sample to be analyzed will be composed of 60 eyes.

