#### Duration of treatment: 10 days

#### Reference product, dose and route of administration, lot:

- 1. **Xyel Ofteno**®. Xantana gum 0.09% / Chondroitin sulfate 0.1% / preservative-free ophthalmic solution. Prepared by Sophia Laboratories, S.A. of C.V., Zapopan, Jalisco, Mexico.
  - a. Dosage: 1 drop 4 times a day during the waking period, both eyes
  - b. Route of administration: topical ophthalmic
- 2. **Systane Ultra®.** Polyethylene glycol 400 0.4%, propylene glycol 0.3%. Prepared by Alcon Laboratories, Inc.
  - a. Dosage: 1 drop 4 times a day during the waking period, both eyes
  - b. Route of administration: topical ophthalmic

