#### Security call / Day 13.

It can be done in a period  $\pm 1$  day in relation to the 13th day of the start of application.

- 1. Ask about the presence of an adverse event.
- 2. Evaluation of results of laboratory tests

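### The sample size in 6.6.1 uses a 3-month adverse-event rate of 8%, unadjusted, for a 10-day exposure, so the stated 80% power is not supported for this trial

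*Combined protocol and SAP*

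**What the plan says.** Section 6.6.1 bases the sample size on adverse events in one cited study, carried out in 150 subjects "with ophthalmic solutions with Hyaluronate sodium and diquafosol with and without preservative for 3 months". It reports: "The percentage of adverse events that occurred with the preservative-free HS solution was 8". The second proportion appears only in words: "at least more than 60% of the exposed subjects will not present this rate of adverse events". The error rates are given as "With a statistical confidence of 95% corresponding to the type I error, equal to 1.96" and "with a power of 80%, corresponding to the type II error, equal 0.84". The result is 7.6, rounded to 8 per group, or 24 in all, raised by 25% to 30.

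The Summary gives "Duration of treatment: 10 days". Section 6.4.4 makes the last adverse-event contact the "Security call / Day 13" (± 1 day). Section 6.2.1 enrols systemically and ophthalmologically healthy adults aged 18 to 40, whereas the title of reference 46 (section 11) concerns treatment of dry eye syndrome. Section 5.6.1 remarks that the intervention time is short but does not connect this with the 8%. No section says when in the 3 months the events occurred, or why the figure carries over.

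**The concern.** A cumulative proportion belongs to a follow-up time. The 8% built up over 3 months; treatment here lasts about one ninth as long, in a different population. Unless most of those events fell in the first days, 8% is not the rate to expect.

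This matters because adverse events are the only variable on which the trial is sized. They are also a primary safety variable in the 8.3.1 rule that calls PRO-087 safe and tolerable when no clinical or statistical differences from the comparators appear. When few events are expected, a lack of difference in adverse events says little, and a printed 80% power makes it look informative.

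**Working it through.** **Inputs.** From 6.6.1: p1 = 0.08 over 3 months, z = 1.96 and 0.84, n = 7.6 (8) per group. From the Summary: 10 days of treatment, 10 subjects per group. From 6.4.4: last contact day 13. From 8.3.1: Pearson chi-square between groups, alpha 0.05. Assumptions of this check: 3 months = 90 days; p2 = 0.64, which is back-solved and not printed.

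**1. The plan's own figure.** The standard unpooled form is n = [p1(1−p1) + p2(1−p2)](1.96 + 0.84)² / (p1 − p2)².
- p2 = 0.64: (0.0736 + 0.2304) × 7.84 / 0.3136 = 7.60, which matches.
- p2 = 0.60: (0.0736 + 0.2400) × 7.84 / 0.2704 = 9.09, which does not.

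So 0.64 fits the stated result and the wording about more than 60%, but it remains an inference.

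**2. The 8% on this trial's time scale.** At a constant hazard, p(t) = 1 − (1 − 0.08)^(t/90).
- Day 10: 1 − 0.92^(10/90) = 0.92%. Taking 3 months as 84 or 92 days gives 0.99% or 0.90%.
- Day 13: 1 − 0.92^(13/90) = 1.2%.

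If the first 10 days carry a fraction f of the 3-month cumulative hazard, the rate is 1 − 0.92^f: 2.1% for f = 0.25, 4.1% for f = 0.50, 6.1% for f = 0.75.

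**3. Expected events.**

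| Rate | Per group of 10 | Of 30 | Chance of no event in 30 |
|---|---|---|---|
| 8% as entered | 0.8 | 2.4 | 0.92^30 = 8% |
| 0.92% (day 10, constant hazard) | 0.09 | 0.28 | 0.9908^30 = 76% |

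**4. Effect on power.** Exact power is the sum of the two binomial probabilities over all tables in which the uncorrected Pearson chi-square reaches 3.84. At either size, an arm with no events needs at least 4 events in the other: with 10 per group, 0 against 4 gives 5.0 and 0 against 3 gives 3.5.

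| Reading, with p2 = 0.64 | Rates compared | Power, 8 per group | Power, 10 per group |
|---|---|---|---|
| Sponsor's inputs | 8% vs 64% | 74% | 78% |
| Only the 8% rescaled | 0.92% vs 64% | 87% | 95% |
| Both are 3-month risks, constant hazard | 0.92% vs 10.7% | 0.6% | 1.5% |

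Here 10.7% = 1 − 0.36^(10/90). If both are 3-month risks with early onset, power with 10 per group is 14%, 46% and 66% for f = 0.25, 0.50 and 0.75.

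**5. What the fixed size can show.** With zero events in n subjects, the one-sided 95% upper limit is 1 − 0.05^(1/n): 26% for n = 10, 31% for n = 8. With a comparator rate near 1%, the same exact test has 80% power only if the other arm's rate is about 51% (10 per group) or 60% (8 per group).

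**The case against.** The strongest reply is that the calculation compares two proportions and is driven by the very large contrast with p2, not by the number of reference events. Correct only the input known to be mismatched and the trial looks better powered: the unpooled n falls from 7.6 to 4.7, and the rate detectable with 80% power at 10 per group falls from about 66% to 51%. Part of the shortfall at the sponsor's own inputs (74% and 78%) comes from the approximate formula, not from follow-up time. All of this stands. A reader might infer from the short exposure that the trial has almost no power. That needs p2 to be a 3-month risk as well as a constant hazard, and the documents say neither.

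Second, events may come early. The subject's diary asks about burning, foreign-body sensation, red eye and itching after each instillation (6.4.3.9), so much of the 8% could fall within 10 days. This also stands as a possibility, and it is why a range is given. It does not justify the carry-over, because the plan offers no time course.

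Third, the design is exploratory phase I, and the rule in 8.3.1 covers all primary variables, not adverse events alone. That limits the consequence, but the power figure is still printed with no such caveat.

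**Conclusion.** The point holds as a defect in a printed input. An 8% proportion accumulated over 3 months, in a dry-eye study by its title, is used without adjustment or justification as the per-subject rate for healthy people treated for 10 days. The 80% power with 8 per group is therefore not supported for this trial.

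The size depends on assumptions. The comparable rate is about 0.9% to 1.2% under a constant hazard and 2.1% to 6.1% under the early-onset cases tried. The direction of the effect on power is undetermined until p2 and its period are stated.

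Two further inferences are tempting but go too far. One is that adverse events cannot be expected at all: this rests on a constant hazard, and even then there is about a 24% chance (100% − 76%) of at least one event among 30 subjects. The other is that a finding of no difference is close to guaranteed: this depends also on PRO-087's true rate, which is unknown.

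**What to change.** In 6.6.1:
- Put the reference rate on the 10- to 13-day scale, showing the hazard assumption and an early-onset range, or justify using 8% unchanged in healthy subjects.
- State p2 as a number, with the period it refers to.
- Replace the 80% power claim with the limits and detectable rates in step 5 of the working.

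In 8.3.1, report adverse events per subject with exact limits (the section now counts eyes), and confine the conclusion to 10-day exposure.

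Keep 30 subjects. The cost is rewording in two sections, with no added subjects, visits or procedures. The downside is that the stated figure becomes less favourable.

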# 8.3 Statistical methodology

#### 8.3.1 Analysis of primary and secondary outcome variables.

The statistical analysis will be carried out by personnel from Sophia Laboratories, S.A. of C.V The statistical program SPSS version 19 (IBM Corporation, Armonk, NY, USA) will be used.

The designated personnel will be blinded to the intervention groups. The coding will be done using consecutive numbers for each intervention group.

The data will be collected and sorted in an excel sheet. Later they will be exported to the platform of the SPSS program. The variables will be categorized according to their nature.

CONFIDENTIAL

The result of the continuous quantitative variables will be presented in measures of central tendency: media, standard deviation and ranges. **See Table 5**. Scales to be used

The normal distribution of the results will be obtained by the Kolmogorov-Smirnov test.

The statistical analysis of the continuous **quantitative variables** to find significant differences (p) will be the following:

- Intra-group analysis: Wilcoxon rank test.
- Inter-group analysis: Kruskal-Wallis test.

The level of difference to consider significance will be an alpha of 0.05 or less.

The result of nominal and ordinal qualitative variables will be presented in frequencies, proportions and percentages. See table 1 (section 6.4.3).

The statistical analysis to identify significant differences of the **qualitative variables** will be done by creating 2x2 contingency tables and will be done as follows:

- • Intra-group difference: McNemar test.
- • Difference between groups: χ2 test (Chi-square) of Pearson.
- The level of difference to consider significance will be of an alpha of 0.05 or less.
- For the reporting of adverse events all eyes of those participants who were randomly assigned to an intervention group after the baseline visit will be considered. The results will be expressed in number of cases (eyes).
- The final report of the results will be shown in tables or graphs, as appropriate.
- It will be considered that the investigational drug is safe and tolerable when there are no clinical and statistical differences in all the variables of primary outcome, with respect to its comparators.

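### Section 6.6.1: the 7.6 (8) subjects per group for 80% power does not follow from the figures given, because neither proportion is defined

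*Combined protocol and SAP*

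**What the plan says.** All of the inputs are in section 6.6.1 of the combined protocol and SAP.

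- Event rate, from a cited comparative study: "The percentage of adverse events that occurred with the preservative-free HS solution was 8" per cent.
- The only other rate: the sponsor expects that "at least more than 60% of the exposed subjects will not present this rate of adverse events".
- Type I error: "With a statistical confidence of 95% corresponding to the type I error, equal to 1.96".
- Power: "with a power of 80%, corresponding to the type II error, equal 0.84".
- Result: "According to the previous calculation, the result is 7.6 subjects (8) per group". Three groups make 24, "which was increased by 25% due to the probable losses", giving 30 subjects, or 10 per group.

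The formula is introduced as one for proportions. As printed it uses products of p1 and p2 and has no (1 − p) terms. Neither symbol is given a value.

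On the analysis, section 8.3.1 says that testing of qualitative variables "will be done by creating 2x2 contingency tables and will be done as follows", with Pearson's chi-square between groups. For adverse-event reporting, "all eyes of those participants who were randomly assigned to an intervention group after the baseline visit will be considered", and results are expressed as numbers of eyes.

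**The concern.** A two-proportion sample size needs two proportions, and this section identifies neither. The 8% can reasonably be taken as one of them. The 60% sentence cannot be taken as the other without guessing: it speaks of subjects who will not show a rate, so it might mean p2 = 0.60, its complement 0.40, or some value above 60%. A reader therefore cannot tell what difference the trial was sized to detect, or check the claimed 80%.

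At stake is how much weight a non-significant adverse-event comparison can carry. A reader who accepts 80% power will read such a result as moderately reassuring. That reading has no basis until the difference being detected, the test and the unit of analysis are known.

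**Working it through.** **Inputs.** From section 6.6.1: p1 = 0.08 (assumed to be the 8% rate), z = 1.96 and z = 0.84, so (1.96 + 0.84)² = 7.84. Because p2 is not stated, it is tried at 0.60, at the complement 0.40, and at the value that returns 7.6.

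**Step 1: formula as printed**, reading the first z term as 1.96: n = p1·p2·(1 + 7.84)/(p1 − p2)².
- p2 = 0.60: 0.048 × 8.84/0.2704 = 1.57
- p2 = 0.40: 0.032 × 8.84/0.1024 = 2.76

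Neither is near 7.6. The formula may have been damaged in translation or in reading the PDF, so little weight is put on this step.

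**Step 2: standard unpooled formula**, n = [p1(1 − p1) + p2(1 − p2)] × 7.84/(p1 − p2)².
- p2 = 0.60: (0.0736 + 0.2400) × 7.84/0.2704 = 9.09, so 10 per group
- p2 = 0.40: (0.0736 + 0.2400) × 7.84/0.1024 = 24.01, so 25 per group
- p2 = 0.64: (0.0736 + 0.2304) × 7.84/0.3136 = 7.60, so 8 per group

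The plan's figure is reproduced at p2 = 0.64. Within this formula, only values from about 0.639 to 0.641 round to 7.6.

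**Step 3: is 0.64 the only route to 7.6?** No. With the same two z values, the pooled formula reaches 7.6 at p2 = 0.732, the arcsine formula at 0.713 and the formula as printed at about 0.225. None of these values is stated either.

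**Step 4: remaining arithmetic.** 8 × 3 = 24 and 24 × 1.25 = 30. This is correct as described.

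**Step 5: power if 8% versus 64% was intended**, a difference of 64 − 8 = 56 percentage points.

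The normal approximation behind the unpooled formula is Φ(0.56·√n/√0.304 − 1.96). It gives Φ(0.913) = 82% at n = 8 and Φ(1.252) = 89% at n = 10. On its own terms, then, the 80% is met.

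Exact power was obtained by enumerating independent binomial counts per subject at the 0.05 critical values, 3.841 (1 df) and 5.991 (2 df):

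| Test, no continuity correction | n = 8 | n = 10 |
|---|---|---|
| Pairwise 2x2 Pearson | 74% | 78% |
| 3x2 Pearson, one arm at 64%, two at 8% | 80% (79.8%) | 87% |
| 3x2 Pearson, one arm at 8%, two at 64% | 75% | 81% |

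The n = 8 column is the calculated size and n = 10 is the enrolled size.

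**Step 6: precision of 10 per group.** With 0 events in 10 subjects, the two-sided 95% upper limit is 1 − 0.025^(1/10) = 31%.

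**The case against.** The strongest reply is that this is a reporting gap and not a miscalculation. The 60% sentence refers to more than 60%, and 0.64 is compatible with that. The unpooled formula with 0.64 gives exactly 7.60. On this view 0.60 is only a boundary, and testing the plan at 0.60 tests an input that it never claims. This largely stands: once 0.64 is supplied the arithmetic is sound. But the value is not supplied, and a stated result still has to follow from stated inputs.

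A second reply is that any power shortfall depends on a test that the reviewer has chosen. This also stands. Section 8.3.1 names 2x2 tables in a three-group trial without saying that comparisons are pairwise, and it counts adverse events in eyes. The Summary's statistical methodology names only a chi-square test. At 10 per group the three-group test exceeds 80% in both configurations, and the pairwise test falls short by about 2 points. Planning with a normal approximation is also ordinary practice.

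A third reply is that an exploratory phase I trial needs no power calculation, and section 6.6.1 itself says that references for one are lacking. That limits the consequence. It does not remove the defect, because the plan chose to make the calculation and to claim 80%.

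**Conclusion.** Wrong as written, with minor consequence. No rate stated in section 6.6.1 returns 7.6 per group: the standard unpooled formula gives 9.1 or 24.0, depending on how the 60% sentence is read. This rests on taking the 8% as one of the two proportions and on the stated 1.96 and 0.84. It does not depend on the damaged-looking formula.

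Three stronger readings are tempting, and the documents do not support them.

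- **That the trial was set to detect 8% versus 64%.** This is a plausible reconstruction only, since other formulas reach 7.6 at other unstated values.
- **That the trial falls short of 80% power.** At 8% versus 64% with 10 subjects per group, power runs from 78% to 87% according to the test, and the plan does not fully specify the test.
- **That the allowance for losses is already used up**, because 10 × 3 = 30 at p2 = 0.60. The documents do not give 0.60 as p2, and section 8.3.1 counts all randomised participants for adverse events.

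N, design and analysis do not change.

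**What to change.** Keep N at 30 and revise section 6.6.1 in one of two ways.

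1. **Keep the calculation.** State p1 and p2 as numbers and say which group or scenario each describes. Reword the 60% sentence so that it defines a rate. Print the formula actually used, with its (1 − p) terms. Name the test (pairwise or three-group, with or without correction) and the unit, which should be the subject. Then restate the power of that test at 8 and at 10 per group. If 8% versus 64% was intended, the figures are those in the table above, and the 56-point difference should be stated openly.
2. **Drop the 80% power claim.** Describe 10 per group as a feasibility-based phase I size and give its precision: with no events in 10 subjects, the two-sided 95% upper limit is 31%.

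The cost is the rewording of one section, plus a stated power that may look less favourable, or no power statement at all.

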#### Statistical methodology:

The data will be expressed with measures of central tendency: mean and standard deviation for the quantitative variables. The qualitative variables will be presented in frequencies and percentages. The statistical analysis will be carried out through the Kruskal-Wallis test for quantitative variables. The difference between the qualitative variables will be analyzed by means of X2 (Chi2). An alpha  $\leq$  0.05 will be considered significant.

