# 6.3 Intervention

#### 6.3.1 Managed treatments

- 6.3.1.1 Treatment in study.
  - PRO-087

o Active ingredients (lubricant): chondroitin sulfate 0.18%, sodium hyaluronate 0.1%

- o Pharmaceutical form:
- o Prepared by: Sophia Laboratories, S.A. of C.V.
- o Dosage: 1 drop in both eyes, 4 times a day during the waking period
- o Description of the solution: transparent solution, free of visible particles.
- o Description of container: sterile multi-dose bottle

Type of agent	Quantity mg/mL	Function
Chondroitin sulfate	1.8	Active principle (lubricant)
Sodium hyaluronate	1	Active principle (lubricant)
Boric acid	2.00	Active principle
Sodium borate decahydrate	Without showing	Additive
Polysorbate 80	Without showing	Additive
Sorbitol	Without showing	Additive
Potassium chloride	Without showing	Additive
Sodium chloride	Without showing	Additive

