#### 6.5.1 Procedures to be performed per visit.

#### 6.5.1.1 Scrutiny visit.

- Signature of informed consent: refers to the signing of the written informed consent document. See 10.3 Consent (assent)
- General and ophthalmological clinical history: refers to the technical, clinical and legal document in which the patient's health conditions, medical acts and other procedures performed on the patient are recorded chronologically. It includes the anamnesis and comprehensive ophthalmological exploration that allows to discern the patient's eligibility. If the patient is taken from the established consultation of the study center, he / she will be able to use the existing clinical history, only having to perform an update.
- Taking laboratory samples: see 6.4.3.12 Laboratory tests.
- Pregnancy test: see 6.4.3.11 Pregnancy test.
- Eligibility criteria: refers to the review by the IP, where it states that the subject can be included in the study by meeting the inclusion criteria and not meeting the exclusion criteria. See 6.2 Eligibility criteria
- Intraocular pressure: see 6.4.3.6 Intraocular pressure
- Visual ability: see 6.4.3.1 Visual capacity
- TRL: see 6.4.3.10 Rupture time of the tear film
- Epithelial defects (TF and TVL): see 6.4.3.4.1 Stains
- Eve signs and symptoms: see 6.4.3.4 Eye surface integrity: and 6.4.3.9 Ocular symptomatology
- Subsequent segment; see 6.4.3.7 Subsequent segment
- Vital signs: see 6.4.3.8 Vital signs

6.5.1.2 Basal Visit .

- Review of laboratory tests: refers to the review and analysis by the IP of the results of the BH, QS and PFH. See 6.4.3.12 Laboratory tests.
- Eligibility criteria: with the laboratory results, the subject's profile will be finalized for inclusion or not.
- Assignment: It refers to determining the intervention that the patient will follow during the study. It will be done according to section 7. Methods. Assignment of the intervention. This assignment will be made at the baseline visit (day 0) and will go along with the indication to start the treatment period the next day (day 1).
- Delivery of intervention: Refers to the delivery of the product under investigation to the patient of the study, by the research center. It will be done according to sections 6.3.1 Managed treatments and 6.3.4.1 Delivery and reception.

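### Both eyes of a subject receive the same product but are analysed as 60 independent eyes; for intraocular pressure the nominal 5% Kruskal-Wallis level becomes about 10–24% at assumed between-eye correlations of 0.3–1.

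*Combined protocol and SAP*

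**What the plan says.** - **Allocation is by subject.** Section 6.5.1.2 (Basal Visit) describes assignment thus: "It refers to determining the intervention that the patient will follow during the study".
- **Both eyes get the same product.** Section 6.3.1.1 has "Dosage: 1 drop in both eyes, 4 times a day during the waking period", and the two comparators in 6.3.1.2 are given in the same way.
- **Sample size is in subjects, analysis is in eyes.** Section 6.6.1 derives 8 subjects per group, raises the total to 30 for losses, and then describes subjects "who will provide both eyes for the analysis, so that the total sample to be analyzed will be composed of 60 eyes".
- **Tests.** Section 8.3.1 gives, for continuous variables, "Inter-group analysis: Kruskal-Wallis test". The Summary is broader: "The statistical analysis will be carried out through the Kruskal-Wallis test for quantitative variables". For qualitative variables the analysis in 8.3.1 "will be done by creating 2x2 contingency tables", with Pearson's chi-square between groups. The level is 0.05 throughout.
- **Adverse events.** Section 8.3.1 reports them as numbers of eyes.
- **Decision rule.** The product is called "safe and tolerable when there are no clinical and statistical differences in all the variables of primary outcome" relative to its comparators (8.3.1).

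Sections 8.3.1 to 8.3.3 do not average the two eyes, select one, or name a method for paired eyes. Section 8.3.2 carries the same methods into the partial analysis of 3 subjects per group.

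**The concern.** Kruskal-Wallis and Pearson chi-square both assume independent observations. Two eyes of one person on one product are not independent, so 20 eyes per arm carry less information than 20 people would. Treating them as independent understates the variability between arms, and the test rejects too often.

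The variables are not all affected alike:

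- **Affected, primary:** intraocular pressure; staining grade; visual ability; hyperemia; chemosis; adverse events counted by eye. Staining grade is typed as discrete in Table 5, so Kruskal-Wallis covers it under the Summary but not clearly under 8.3.1.
- **Affected, but secondary and so outside the safety rule:** tear rupture time.
- **Depends on an unstated unit:** goblet cell density (6.4.3.2 refers to a single eye to be evaluated) and the questioned symptoms (6.4.3.9 does not say per eye or per subject).
- **Not affected:** laboratory tests, vital signs and the comfort index.

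At stake is the statistical half of the safety rule, which does not run at its stated level for eye-level variables. Counting adverse events in eyes also counts a bilateral event twice, does not fit a systemic event, and uses a denominator that does not match the sample size. The within-arm Wilcoxon and McNemar tests have the same fault but do not enter the rule.

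**Working it through.** **1. The plan's own figures.** 8 subjects × 3 groups = 24; 24 × 1.25 = 30 subjects; 30 × 2 = 60 eyes. The loss allowance and the total are in subjects; only the last step moves to eyes.

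**2. Inputs.** Three arms, 10 subjects per arm, two eyes per subject on the same product, Kruskal-Wallis on 2 degrees of freedom, 5% critical value 5.991. The between-eye correlation ρ is not in the documents and is varied.

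**3. Approximate formula.** With two eyes per subject, the variance of an arm's mean rank grows by about (1 + ρ). The statistic then behaves like (1 + ρ) times a chi-square on 2 degrees of freedom, and the true level is about exp(−5.991 / [2(1 + ρ)]). At ρ = 0.5 this is exp(−5.991/3) = 0.136.

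**4. Simulation with identical products.** Normal data, at least 20,000 trials per setting. Repeat runs agree within about half a percentage point.

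| ρ | Formula | Kruskal-Wallis on 60 eyes |
|---|---|---|
| 0 | 5.0% | 4.9% |
| 0.3 | 10.0% | 9.7% |
| 0.5 | 13.6% | 13.3% |
| 0.8 | 18.9% | 19.0% |
| 1 | 22.4% | 23.5% |

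Kruskal-Wallis on the 30 subject means rejects in 4.6–4.7% of the same trials. Rounding pressure to whole mmHg (assumed mean 15, SD 2.5) changes nothing material. With 8 subjects per arm, the eye-level range for ρ from 0.3 to 1 is 9.5–23.7%.

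**5. Mostly-zero three-level grade.** Here ρ is on an underlying normal scale, and 70% of non-zero eyes are assumed to be at the lower grade. Eye-level Kruskal-Wallis at ρ = 0.3, 0.5 and 0.8 rejects in 4.3%, 5.0% and 8.0% of trials with 95% of eyes at zero, and in 6.3%, 8.3% and 13.3% with 85% at zero. Using the worse eye per subject gives 2.6–4.9%.

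**6. Present/absent sign, Pearson 2×2 on 20 eyes per arm.** Exact enumeration, with ρ on the binary scale:

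| Event rate | ρ = 0.5 | ρ = 1 |
|---|---|---|
| 1% | 0.2% | 0.8% |
| 2% | 0.8% | 2.6% |
| 3% | 1.8% | 5.1% |
| 5% | 4.1% | 10.4% |
| 8% | 7.4% | 16.8% |

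There is no real inflation at 3% or below. It is clear only with high correlation at rates near the 8% adverse-event figure used in 6.6.1.

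**7. Double counting, an illustration.** Suppose 2 of 10 subjects in one arm have a bilateral event and none do in another. By eye, 4/20 vs 0/20 gives Pearson p = 0.035. By subject, 2/10 vs 0/10 gives Pearson p = 0.14 (Fisher 0.47). The same two people cross the 0.05 line only when counted by eye.

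**8. Direction.** These are false differences somewhere among the three arms. In about one third of the false Kruskal-Wallis rejections the two comparators are the extreme pair and PRO-087 lies between them.

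**The case against.** The case for a milder view has six parts.

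- **Wording.** Section 8.3.1 does not repeat the word eyes beside Kruskal-Wallis. But 6.6.1 defines the analysed sample as 60 eyes and nothing reduces it to one value per subject. If subject-level analysis was meant, 6.6.1 is wrong and needs correcting anyway.
- **Assumed correlation.** No document supports a floor of 0.3, ρ = 1 is an extreme, and changes in pressure may correlate differently from raw readings. That is fair, but ρ of 0.1 and 0.2 still gives about 6.5% and 8.0%, and the fix works without knowing ρ.
- **Relevance to PRO-087.** Leaving out rejections where the comparators are the extreme pair, the rates fall to about 6.3%, 9.1%, 12.3% and 15.5% at ρ = 0.3, 0.5, 0.8 and 1. This stands as a qualification.
- **Dilution.** Table 5 lists 25 laboratory variables, all primary. If 15 to 25 of them acted as independent 5% tests, the chance of at least one false laboratory difference would already be 1 − 0.95^15 = 54% to 1 − 0.95^25 = 72%. Moving pressure from 5% to 13% would raise the chance of any false difference only from 56% to 60%, or from 74% to 76%. The effect on the whole rule is therefore modest. Multiplicity is a separate fault, however, and does not make the eye the right unit.
- **Caution.** In an exploratory phase I safety study a false alarm is the cautious error, and a subject-level test rejects less often. This also stands, and is a reason not to read non-significance as similarity.
- **Adverse events.** The sentence on eyes concerns reporting and names no test, and subject code and eye are recorded (9.3.1.1). Counts by subject can be recovered, but the plan should ask for them.

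**Conclusion.** The concern holds. The plan assigns by subject, analyses by eye, and applies tests that ignore the pairing. For a roughly continuous eye-level variable, of which intraocular pressure is the clear primary example, the stated 5% level is about 10% at ρ = 0.3 and 24% at ρ = 1. It exceeds 5% at every positive correlation examined. The effect is smaller for mostly-zero grades and negligible for signs at 3% or below. These sizes rest on assumed correlations, assumed sign rates and normal data; the mismatch between the unit of allocation and the unit of analysis rests on the documents alone. The error runs towards a false difference and against a finding of safe and tolerable. It should be corrected before the data are analysed.

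**What to change.** **Change**

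- In 8.3.1, make the subject the unit of analysis (n = 30) for every eye-level variable. Use the mean of the two eyes for continuous variables, and one prespecified per-subject summary, such as the worse eye, for graded or present/absent signs. An eye-level model that allows for clustering, with a named small-sample correction, is an acceptable alternative.
- Report adverse events as subjects with at least one event plus the number of events, listing laterality.
- In 6.6.1, replace the 60-eye statement with 30 subjects, both eyes measured.
- State whether cytology and the questioned symptoms are recorded per eye or per subject.
- State that a non-significant result is not by itself evidence of similarity.

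**Cost.** Wording in 6.6.1 and 8.3.1 and a short data step; no new subjects or measurements. The sample size was set in subjects, so the number of subjects does not change.

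Nominal detection falls. The table shows Kruskal-Wallis detection of a true 1-SD shift in one arm:

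| ρ | By eye, nominal 5% | By eye, held to a true 5% | Subject means |
|---|---|---|---|
| 0.3 | 87% | 79% | 74% |
| 0.5 | 85% | 71% | 67% |
| 0.8 | 85% | 63% | 59% |

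Most of the drop is power the eye-level test never honestly had; the real loss is about 4 points. Subject-level 2×2 tests with 10 per arm are also conservative (Fisher first reaches 0.05 at 5/10 vs 0/10, p = 0.033), so event counts should be read descriptively. The change restores the level of each eye-level test; it does not address the number of primary variables tested together.
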